RESEARCH PROTOCOL

I. TITLE Prevention of Post Intensive Care Syndrome in Family with SAF-T Intervention: Feasibility Study

II. STAFFING

| Name and Title | Responsibility | Address | Phone Number |
|----------------------------|------------------------|----------------------|----------------|
| [name], MSN | Principal Investigator | USF | [contact] |
| Jonas Leader PhD Scholar | | [name] | |
| USF College of Nursing | | [name] | |
| | | [name] | |
| [name], ANP-C, | Co-Investigator | USF | [contact] |
| PhD, FAAN | | [name] | |
| USF College of Nursing, | | [name] | |
| Associate Dean of Research | | [name] | |
| and Innovation | | | |
| [name] | Regulatory Specialist | USF | [contact] |
| | | [name] | |
| | | [name] | |
| | | [name] | |

III. CONFLICT OF INTEREST

None of the investigators will benefit from participants' participation in this project or completion of the project in general.

IV. RESOURCES

Sigma Theta Tau International Honor Society of Nursing - Delta Beta Chapter-at-Large

V. HYPOTHESIS

In the ICU, spouses often find themselves in a stressful environment, expected to manage surrogate health decisions for their critically ill loved one. Evidence in the literature suggest higher stress levels experienced by spouses in the ICU environment, increases their risk for Post Intensive Care Syndrome (PICS).^{3,4,12,14,17,18,28,34,41} Reducing stress in the spouse during the ICU hospitalization may reduce their likelihood of PICS. We hypothesize that participants who receive the Sensation Awareness Focus Training (SĀF-T) intervention will experience less PICS than control participants who do not receive the intervention.

VI. SPECIFIC AIMS

The primary specific aim of the proposed project is to test the feasibility and determine effect size of the S $\overline{A}F$ -T intervention on PICS, specifically spouses of critically ill, mechanically ventilated patients. We will carefully examine the ability of participants to adequately perform S $\overline{A}F$ -T and adhere to the study protocol. A secondary aim of this project is to explore if the effect of S $\overline{A}F$ -T and sleep/rest are related. Findings from this feasibility study will be used to design a dissertation study with adequate power to test S $\overline{A}F$ -T.

VII. BACKGROUND AND SIGNIFICANCE

Significance

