IX. RESEARCH DESIGN AND METHODS

Research Design

We will use a prospective, randomized, experimental design to accomplish the specific aims. Participants (n=10) will be randomly assigned within 36 hours of the patient's ICU admission and intubation to one of two groups. The intervention group will receive the SAF-T intervention daily, over a 3-day period (72 hours) or until discharge of the patient from the ICU, if discharged within 3 days. The control group will not receive the SAF-T intervention. Usual care for spouses of critically ill patients will continue for both groups. **Sample.** A feasibility sample size of 10 participants will be randomly assigned (using a blocked design) to two groups (n=5 intervention group, n=5 control group). Eligibility criteria: spouses of patients intubated and

admitted within 36 hours to the adult ICUs are expected to remain in the ICU at least 36 hours, and spouse is aged 18 years or older, and is able to understand English. Exclusion criteria: anticipation by the clinical provider of imminent patient death, spouse does not understand English, under the age of 18 years old, or is actively being treated for a PICS condition (anxiety, depression, PTSD).

Setting. Participant recruitment, enrollment, and interventions will be conducted at Tampa General Hospital (TGH), a level I trauma center with 225 critical care beds. During past and current studies, we have established excellent research relationships at TGH, as both principal investigator (PI) [name] and her USF faculty adviser/co-investigator [name] are credentialed by TGH Office of Clinical Research.

Methods

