
2) Control Group: The control group will consist of usual care. There will be no SĀF-T intervention, but participants will continue to receive support by care providers, as part of usual care practices (orientation to ICU patient room and ICU waiting room, use of bathroom and shower in patient's room, review of ICU visiting policy with contact information, optional guest food tray and other onsite locations to acquire food and beverages, clean towels, warm blankets, and resources for spiritual support), which may reduce their level of stress. Participants will remain in the study in the ICU over 3-days (72 hours) or until discharge of the patient from the ICU, if discharged within 3 days.

Key Variables and Their Measurement

Following study enrollment and signed consent, key variables will be collected from participants, as outlined in Table 1.

D .

| Table 1 | | | |
|----------------|-----------|----------|------------|
| Key Variables, | Measures, | and Data | Collection |

| | | Data Collection Time Points | | | Points |
|---|--|-----------------------------|----------------|-----------------|-----------------|
| Concept | Measures | Study Day 1 | Study Day 3 | Study Day 30 | Study Day 90 |
| PICS-F | | 2 wj 1 | 2 wj c | 2 4 9 0 0 | 2 4 9 9 0 |
| -Symptoms of Anxiety -Symptoms of Depression | Hospital Anxiety and Depression Scale (HADs) | * | * | * | * |
| -Symptoms of PTSD | Impact Event Scale (IES) | * | * | * | * |
| Stress | Perceived Stress Scale (PSS) | * | * | * | * |
| Sleep/Rest | Actigraphy (continuous over a 3-day period in ICU) | * | | | |
| Behavior Function Demographic | NIH Toolbox Emotion Battery | * | * | * | * |
| Characteristics | Age, race, ethnicity, sex, history of PICS-F conditions, level of education, & distance of hospital commute | * | | | |

_

C 11

. .

—·

PICS-F. The measures for symptoms of PICS-F conditions (anxiety, depression, and PTSD) are found in the literature associated with spouses of adult ICU survivors.

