Data Management. Data will be downloaded into research electronic data capture (REDCap), a secure web application database, which will be accessed by a secure USF web connection with authentication and data logging. A unique identifier will be assigned to each participant by the PI in the database to conceal their identity on all research data. The data files will be backed up daily during the data entry process and once a week during other times by the PI. All data files will be housed on the university server, which is backed up every 24 hours and copies, are stored off-site for additional security. Access to the database will be password protected and limited to the investigators.

X. PLAN FOR CONTROL OF INVESTIGATIONAL DRUGS, DEVICES, AND BIOLOGICS N/A

XI. DATA ANALYSIS PLAN

Data Analysis

The defining parameter for feasibility is a minimum of two days participation in the study. Descriptive statistics will be reported as means +/- standard deviation for continuous variables and as frequencies and percentages for categorical variables. We will perform repeated measures models in order to compare symptoms of PICS-F conditions in the intervention and control groups. Specifically, the repeated outcome variables (symptoms of anxiety, depression, & PTSD) will be modeled using generalized linear mixed effects models to account for within-participant variations.³⁵ Estimates of treatment effects (differences between intervention and control groups) will be summarized with odds ratios and corresponding 95% confidence intervals. Our sample size of 10 participants is reasonable for a feasibility study and perform a power analysis for sample size and effect size for the larger dissertation study to follow. A timeline for the feasibility study is provided in Table 2.

Table 2

Timeline for Proposed Feasibility Study

| | Month | Month | Month | Month | Month | Month |
|----------|-------|-------|-------|-------|-------|-------|
| Activity | 1 | 2 | 3 | 4 | 5 | 6 |

| Participant Recruitment & Enrollment | | | |
|---|--|--|--|
| Participant 1 and 3 month follow up | | | |
| Data collection | | | |
| Data management | | | |
| Analysis of final results | | | |
| Prepare dissertation study | | | |
| Final results manuscript | | | |

XII. DATA AND SAFETY MONITORING

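### The only feasibility criterion is a per-person minimum of two days in the study: it defines no failing result, can be met by controls who receive no SAF-T, and names no denominator

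*Combined protocol and SAP*

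**What the plan says.** Section VI (Specific Aims) states that the primary aim is to "test the feasibility and determine effect size of the" SAF-T intervention. It adds that the investigators will examine how well participants perform SAF-T and "adhere to the study protocol", and that the findings will be used to design an adequately powered dissertation study.

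Section XI (Data Analysis) gives one criterion: "The defining parameter for feasibility is a minimum of two days participation in the study". On size it says "Our sample size of 10 participants is reasonable for a feasibility study", with no target rate or precision.

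Section IX allocates five spouses to each arm. Of the controls it says "The control group will not receive the SAF-T intervention" and "The control group will consist of usual care". Controls stay in the study for the same three-day ICU period, or until the patient leaves the ICU if that is sooner.

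Section XVI (Recruitment and Informed Consent) says that when a participant withdraws, no further data are collected and that participant's data forms are destroyed.

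**The concern.** A test of feasibility needs a rule that turns ten individual results into a conclusion. Section XI supplies the individual part (two days) and omits the rest: the number required, the arm, and the denominator. No other section supplies them. Section VI promises to look at performance of SAF-T and adherence, but the analysis plan has no measure or cut-off for either.

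The criterion also concerns time in the study, not exposure to SAF-T. A control's two days show that spouses tolerate enrolment, the actiwatch and the questionnaires. They do not show whether SAF-T can be delivered to, or performed by, a spouse in the ICU.

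At stake is the step to the dissertation study. The bar could be chosen after the data are seen, and low uptake in the SAF-T arm could sit behind a good overall figure.

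**Working it through.** **Inputs from the documents.** N = 10, 5 per arm (section IX); a per-person minimum of two days (section XI); no SAF-T for controls (section IX); forms destroyed on withdrawal (section XVI). The plan gives no feasibility rate, threshold, power or precision, so it has no figure of its own to reproduce. All rates and thresholds below are assumptions for illustration.

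**1. The unstated number decides the verdict.** Let a proportion p of spouses reach two days. The probability that at least r of n do so is the sum over k = r to n of C(n,k) p^k (1−p)^(n−k). With n = 10 and p = 0.60 in both arms:

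| Number required | Probability of passing |
|---|---|
| 1 of 10 | above 0.999 |
| 5 of 10 | 0.834 |
| 7 of 10 | 0.382 |
| 8 of 10 | 0.167 |
| 10 of 10 | 0.006 |

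**2. What pooling would do.** If all 5 controls stay two days and x of the 5 SAF-T spouses do, the pooled count is 5 + x.

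| SAF-T arm | Exact 95% CI | Pooled |
|---|---|---|
| 0/5 | 0% to 52.2% | 5/10 |
| 2/5 | 5.3% to 85.3% | 7/10 |
| 3/5 | 14.7% to 94.7% | 8/10 |
| 4/5 | 28.4% to 99.5% | 9/10 |

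**3. How far this depends on the controls.** Take a true SAF-T rate of 50% and an assumed pooled bar of 8/10.
- All controls stay: the bar becomes X ≥ 3 of 5, so the pass probability is (10 + 5 + 1)/32 = 0.500.
- 95% of controls stay: 0.426.
- 90% of controls stay: 0.359.
- 50% of controls stay: 0.055.

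**4. A rule in the SAF-T arm alone.** For 4 of 5, P = 5p⁴(1−p) + p⁵.
- p = 0.50: 6/32 = 0.188.
- p = 0.70: 0.360 + 0.168 = 0.528.
- p = 0.90: 0.328 + 0.590 = 0.919.

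**5. Denominator and early discharge.** Because withdrawn participants' forms are destroyed, a spouse who leaves on day 1 could disappear from the count or stay in it as a failure; the plan does not say which. Eligibility expects an ICU stay of at least 36 hours, which is less than two full days (48 hours), and the ICU phase ends at the patient's discharge. A spouse can therefore miss two days for a reason unrelated to the acceptability of SAF-T.

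**The case against.** The strongest reply has four parts.

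- *This is a small study meant to inform a design, not a stop/go gate.* That stands as a limit on how firm any rule can be: a 4-of-5 bar rejects a true 70% rate 47% of the time (1 − 0.528). It does not excuse the gap, because the plan itself names a defining parameter and then leaves it incomplete.
- *Control retention is part of feasibility.* It is. The study pilots a randomised design, and the publication plans list the feasibility of longitudinal follow-up as an expected output. This argues for reporting control retention, but separately.
- *The plan does intend to look at SAF-T uptake.* Section VI says so, and performance of SAF-T can be judged only in that arm. But no measure of it reaches section XI.
- *Pooling is nowhere stated.* Correct. Section XI refers to participation in the study, and section IX keeps controls in the study, so controls can meet the criterion. That the arms would be combined into one figure is an inference.

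A reader might go further and infer that no result could fail the primary aim, or that controls receive nothing. The documents support neither. A count of 0/10 would fail on any sensible reading, and the aim also includes an effect size that this criterion does not govern. Controls receive usual care, the actiwatch and all assessments; what they do not receive is SAF-T.

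**Conclusion.** The concern holds in this form: the sole feasibility criterion sets no failing result in advance, can be met without SAF-T, and has no stated denominator. As written, it cannot soundly answer the question in section VI.

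The masking in step 2 (3/5 reading as 8/10, and 0/5 as 5/10) assumes pooled arms and full control retention. A reader might also set the 0.500 pass rate of a pooled 8/10 bar against the 0.188 of a 4-of-5 SAF-T-arm bar and take the difference as the size of the defect. That goes too far. The plan states neither bar, the pooled one is looser in this case only because all controls are assumed to stay, and with 50% in both arms it passes just 0.055 of the time. What does not depend on these assumptions is that the number, arm and denominator are missing.

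**What to change.** Before first enrolment, replace the sentence in section XI with text to this effect:

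> Feasibility of SAF-T is assessed by the number of the 5 spouses randomised to SAF-T who complete a SAF-T session on at least two study days. Spouses who withdraw remain in the denominator and count as not meeting the criterion. The count is reported with its exact 95% confidence interval and compared with a required number of [to be fixed by the investigators]. Two-day study participation among controls is reported separately as retention. Spouses who miss two days because the patient left the ICU early are also reported separately.

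The required number is for the investigators to choose. Four of five is only an example, with the pass probabilities in step 4; the documents do not point to it. Counting completed sessions matters, because a two-day minimum of study participation could be met in the SAF-T arm with no session done. Keeping withdrawals in the denominator needs only a record of allocation and withdrawal, not the destroyed forms.

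The cost is a few sentences and a session log, with no change to sample size or participant burden. The downside is that the figure rests on five people and its interval will be visibly wide, so it should guide the dissertation design and not be read as a firm go/no-go.

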Group Assignment. Randomized assignment will be used to determine the group (intervention or control) for participants. Each participant will have an equal chance of being assigned to receiving the intervention. Usual care by the healthcare team will be provided to both groups (intervention and control). A randomized block design will be used for equal sample size in each group. Randomized group assignment will be generated at randomizer.org and concealed inside opaque, sealed envelopes. Following signed consent, each participant will have an equal chance of receiving the intervention with the opening of a sealed group assignment envelope. **Description of Intervention and Data Collection Procedures.** Data collection will take approximately 30 minutes at four time points: study enrollment, study day 3, study day 30, and study day 90, as shown in Table 1. The actiwatch will take approximately 30 seconds to place on the participant's wrist at the time of study enrollment, which will collect continuous activity and light data over a 3-day period (72 hours) or until discharge of the patient from the ICU, if discharged within 3 days. The SAF-T intervention will take approximately 15-20 minutes each day, over a 3-day period (72 hours) or until discharge of the patient from the ICU, if discharged within 3 days. Descriptions of procedures for each group are as follows. 1) Intervention Group: The SĀF-T intervention includes coaching from SĀF-T trained research staff on awareness of biological sensations associated with events in the ICU that are perceived stressful. Research staff will sit across from the participant and ask them to use their eyes to follow hand movements that will induce lateral left-right (saccadic) eve movements and elicit an orienting response that activates an investigatory reflex in which first, an alert response occurs and then, a reflexive pause produces decreased arousal in the face of no threat.^{5,30,32} The SĀF-T intervention will be administered each day, by trained research staff, over 3-days (72 hours) or until discharge of the patient from the ICU, if discharged within 3 days. The emphasis on the SAF-T intervention on days 2 & 3 will be practicing to independently use the technique as needed by the participant to self-manage stress. Participants will continue to receive usual care practices by care providers (orientation to ICU patient room and ICU waiting room, use of bathroom and shower in patient's room, review of ICU visiting policy with contact information, optional guest food tray, and other onsite locations to acquire food and beverages, clean towels, warm blankets, and resources for spiritual support).

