- Symptoms of Anxiety and Depression. Anxiety is defined as worry or fear that does not go away and interferes with daily activities such as job performance, school work, and relationships.²³ Depression is defined as experiencing signs and symptoms most of the day, nearly every day, for at least two weeks.²³ The Hospital Anxiety and Depression (HAD) scale⁴² will be used to measure anxiety and depression at four time points: study day 1 (immediately prior to first intervention), study day 3, and by telephone interview at study day 30 and study day 90. The HADs is easy to administer and has been successfully used to measure symptoms of anxiety (7 questions) and depression (7 questions) in the general population and in family members of ICU patients.⁴ Scores for each subscale (anxiety and depression) range from 0 to 21 with scores categorized as follows: normal 0–7, mild 8–10, moderate 11–14, and severe 15–21. Although HADs was not designed to be a clinically diagnostic tool, in the event anxiety or depression subscales fall within the severe score range (15-21), the participant will be provided with a copy of their results and encouraged to follow up with their primary care provider for clinical evaluation.
- Symptoms of PTSD. Symptoms of PTSD will be quantified at four time points: study day 1, study day 3, and by telephone interview at study day 30 and study day 90, using the Impact of Event Scale (IES), which is the most commonly used instrument to measure symptoms of PTSD in PICS-F research.⁷ The IES has been widely used for many years and found reliable across a broad range of traumatic events.³⁹ The IES is not a tool for diagnosing PTSD, but instead detects symptoms indicating a risk of PTSD. Each of the 15 items is scored on a 6-point scale rated from 0 to 5; so that the total score can range from 0 to 75.¹⁵ Higher scores indicate more severe post-traumatic stress symptoms. In the event the total IES score is > 30, indicating a high risk of PTSD, the participant will be provided with a copy of their results and encouraged to follow up with their primary care provider for clinical evaluation.

Stress. Symptoms of stress will be quantified at four time points: study day 1 (immediately prior to first intervention), study day 3, and by telephone interview at study day 30 and study day 90, using Cohen's

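### The plan gives the Day 1 symptom score no baseline role and does not say which visits supply the treatment effect

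*Combined protocol and SAP*

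**What the plan says.** Section IX (Symptoms of Anxiety and Depression) schedules the HADS at "study day 1 (immediately prior to first intervention), study day 3, and by telephone interview at study day 30 and study day 90". For the HADS, Day 1 is therefore explicitly a pre-intervention score. The IES paragraph lists the same four days without the remark about the first intervention. That its Day 1 score also precedes treatment is inferred from the procedures text: "Data collection will take approximately 30 minutes at four time points: study enrollment, study day 3, study day 30, and study day 90".

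Section XI states that "the repeated outcome variables (symptoms of anxiety, depression, & PTSD) will be modeled using generalized linear mixed effects models" and that "Estimates of treatment effects (differences between intervention and control groups) will be summarized with odds ratios and corresponding 95% confidence intervals". It mentions no baseline covariate, change score, constrained baseline, visit term or group-by-visit term, and it does not say which visit or visits the group difference comes from. No other section fills this gap.

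The estimate has a declared use. Section VI says "The primary specific aim of the proposed project is to test the feasibility and determine effect size", and adds that "Findings from this feasibility study will be used to design a dissertation study with adequate power to test" the intervention. Section XI repeats the purpose: "perform a power analysis for sample size and effect size for the larger dissertation study to follow".

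**The concern.** Allocation is random and follows consent, so the expected group difference at Day 1 is zero, and a score taken before the first session cannot show a treatment effect. If Day 1 enters as one of four equivalent outcomes under a single group effect, a visit with zero expected effect is averaged into the answer. The reported effect then understates what happened after treatment, and the next study is planned on too small a number.

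Separately, the Day 1 score is the natural tool for removing chance differences between two groups of five, and the plan does not use it that way. Such a difference is random error, not bias, but with 5 per arm its standard error is √(2/5) = 0.63 SD.

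**Working it through.** **Inputs.** From the documents: four visits, the first before treatment; 5 participants per arm; 95% intervals. The documents give no SD, correlation, effect size or power, so there is no figure of the plan's own to reproduce. Assumed here: SD 1 at every visit; within-person correlation ρ of 0.3, 0.5 or 0.7; true effect 0 at Day 1 and 0.80 SD at Days 3, 30 and 90; complete data; two-sided 5% level and 80% power.

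**1. Dilution under one four-visit group effect.** The generalized least squares weights on the visits are 1ᵀV⁻¹/(1ᵀV⁻¹1).
- Random intercept (equal correlations): each visit has weight 1/4. The expected effect is (0+1+1+1)/4 = 75% of the mean follow-up effect at any ρ, so 0.75 × 0.80 = 0.60 SD.
- AR(1) by visit order: weights are proportional to 1, 1−ρ, 1−ρ, 1, so Day 1 has weight 1/(4−2ρ). At ρ = 0.2, 0.5 and 0.8 this is 0.278, 0.333 and 0.417, leaving 72%, 67% and 58% of a constant follow-up effect.
- Random intercept with missing data: 70-71% if 20% are lost after Day 3; 48-59% if 40% are lost after Day 1.
- Unequal visit variances, in the patterns tried: 31-93%.
- Random-intercept logistic model (assumed control event rates of 33% and 70%, intercept SD 1 to 2): 70-76% on the log-odds scale.
- Group-by-visit model with follow-up contrasts: 100%.

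**2. Shift against noise.** The four-visit standard error is √[(2/5)(1+3ρ)/4]. At ρ = 0.5 this is √(0.4 × 0.625) = 0.50, so the shift of 0.80 − 0.60 = 0.20 SD is 0.40 standard errors.

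**3. Planning consequence.** Suppose the diluted effect is carried into a design analysed on the follow-up mean, whose variance is v = (1+2ρ)/3. Then n per arm = 2(1.960+0.842)²v/d².

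| ρ | v | n at d = 0.80 | n at d = 0.60 |
|---|---|---|---|
| 0.3 | 0.533 | 13.1 → 14 | 23.3 → 24 |
| 0.5 | 0.667 | 16.4 → 17 | 29.1 → 30 |
| 0.7 | 0.800 | 19.6 → 20 | 34.9 → 35 |

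Before rounding, the ratio is (0.80/0.60)² = 1.78 throughout.

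**4. What Day 1 buys as a covariate.** With 10 participants the variance of the adjusted follow-up mean is [(1+2ρ)/3 − ρ²] × 7/6, where 7/6 is the small-sample cost of estimating the slope.
- ρ = 0.3: 0.517 against 0.533, 3% less.
- ρ = 0.5: 0.486 against 0.667, 27% less.
- ρ = 0.7: 0.362 against 0.800, 55% less.

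Break-even is where 21ρ² − 2ρ − 1 = 0, at ρ = 0.27.

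**5. Precision that remains.** At ρ = 0.5 the 95% half-widths (t with 8, 8 and 7 degrees of freedom) are 1.15 SD for the four-visit effect, 1.19 for the unadjusted follow-up mean and 1.04 for the adjusted one.

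**The case against.** The strongest reply is that nothing here is a demonstrated error. The text says repeated measures models will compare the groups, and a competent analyst would probably add group-by-visit terms, which removes the dilution. This stands. A reader might infer that the plan will report 75% of the effect. The documents do not support that, because a single four-visit effect is permitted but nowhere stated. Nor is 75% a fixed number: it needs equal correlations and complete data, and visits on Days 1, 3, 30 and 90 are too unevenly spaced to make equal correlation a safe assumption. What the reply does not answer is that a group-by-visit model yields three follow-up effects, and the plan still does not say which one goes into the power calculation.

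A second reply is that ten participants cannot give a usable effect size anyway. This largely stands. At ρ = 0.5, with the adjusted standard error of 0.44, moving one standard error either way from 0.80 (to 1.24 or 0.36) takes the planned size, by the formula and unadjusted variance of step 3, from 7 to 81 per arm. That dwarfs 17 becoming 30. The fix makes the quantity defined and somewhat more precise, but it does not make it reliable.

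Third, a reader might infer that the dissertation study would end up underpowered. The direction is the opposite. If the next study itself analysed the four-visit contrast, planning on 0.60 SD with that contrast's own variance would be consistent, so the 1.78 applies only when the diluted effect is moved into a follow-up-only design.

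Fourth, averaging Days 3, 30 and 90 is only one possible contrast. No section places the Day 3 assessment after the last session, and if the effect began only after Day 3, that mean would show (0+1+1)/3 = 67% of it. This stands, so the choice belongs to the investigators.

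**Conclusion.** The concern holds as a gap in the definition of the effect together with an unused baseline, and it is a cheap improvement. The Day 1 score has no baseline role, and the visits behind the effect size are not named, although that effect size is part of the primary aim.

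The size depends on a choice that the plan leaves open: no dilution with group-by-visit contrasts; 75% in expectation for one four-visit effect under a random intercept and complete data; about 58-72% under AR(1). The planning figures and variance reductions rest on assumed correlations, an assumed 0.80 SD effect and linear-scale scores, so they transfer only approximately to the odds ratios the plan intends to report. The practical gain in this trial is modest. Pre-treatment timing is explicit for the HADS and only inferred for the IES.

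**What to change.** Amend Section XI to state three things:
1. The outcomes are the post-baseline scores.
2. The Day 1 score of the same scale enters as a covariate, or Day 1 stays in the model with the arm means constrained equal there.
3. One post-baseline contrast, chosen and named by the investigators before the data are seen, is the effect used to plan the dissertation study; other visit-specific estimates are descriptive.

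In Section IX, confirm that the Day 1 IES is completed before the first session.

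The cost is analysis wording only, with no new data. The covariate uses one of about 8 degrees of freedom and loses a little precision if its correlation with follow-up is below about 0.27. If yes/no odds ratios are kept, it also raises the risk of separation, where the odds ratio is not finite. In a simulation with 5 per arm, a true odds ratio of 0.33 and assumed visit rates, separation rose from about 3% of trials to 4-9%.

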More than 5.7 million patients are admitted to intensive care units (ICU) each year in the United States.³⁷ The technologically advanced ICU is an unfamiliar frightening environment to patients and their families.¹ Critical

illness is a family crisis. There is strong evidence that family distress in response to critical illness does not disappear after ICU discharge.^{2,4,12,16} The Society of Critical Care Medicine³⁶ has identified a cluster of complications that occur in family members of ICU patients as Post Intensive Care Syndrome-Family (PICS-F). PICS in family members of adult ICU survivors includes symptoms of ongoing anxiety, depression, and post-traumatic stress disorder (PTSD). Data suggest that 70% of family members have symptoms of anxiety and 33% have symptoms of depression and PTSD, which can persist for \geq 4 years.^{7,9,13,24} Moreover, symptoms of anxiety, depression, and PTSD are higher and persist longer in family members than in adult ICU survivors.¹¹ Because PICS-F occurs with greater frequency in spouses and surrogate health decision-makers^{4,27,34} this study will focus on participants whom are spouses of mechanically ventilated critically ill adults (typically sedated and unable to make their own health decisions).

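### Section XI plans 95% confidence intervals from mixed models in ten participants but names no small-sample or separation method, so 95% coverage is not assured

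*Combined protocol and SAP*

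**What the plan says.** IX. Research Design and Methods (Sample) randomises ten spouses in blocks: "n=5 intervention group, n=5 control group". The block size is not given. HADS, IES and PSS are collected on study day 1, "study day 3, and by telephone interview at study day 30 and study day 90", which makes four measurements per participant.

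XI. Data Analysis Plan states that the repeated PICS-F outcomes "will be modeled using generalized linear mixed effects models to account for within-participant variations". It continues: "Estimates of treatment effects (differences between intervention and control groups) will be summarized with odds ratios and corresponding 95% confidence intervals".

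The section does not say:

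- whether the outcomes enter as scores, ordered categories or yes/no variables;
- the link function, the random effects, or which contrast is the treatment effect;
- how the model is estimated, what kind of interval is used, or on how many degrees of freedom;
- what is done if an odds ratio cannot be estimated.

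The instruments allow more than one form. For HADS, "Scores for each subscale (anxiety and depression) range from 0 to 21 with scores categorized as follows" into four bands; for the IES, "the total score can range from 0 to 75", with a high-risk cut above 30.

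**The concern.** Limits from a generalized linear mixed model are commonly large-sample ones: estimate plus or minus 1.96 standard errors. Four visits per spouse do not enlarge the sample for an arm difference averaged over visits. That contrast is between participants and has 10 - 2 = 8 degrees of freedom. A normal multiplier is then too small, and maximum likelihood also understates the between-participant variance. On an odds scale with five per arm there is a second hazard: separation, where the odds ratio or another parameter runs off to infinity.

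Estimating the effect size is part of the primary aim (VI. Specific Aims), and these intervals are the only stated measure of uncertainty for the treatment effect. Limits that are too narrow could make a chance difference among ten people look like support for the hypothesis. An odds ratio that cannot be estimated leaves nothing to report.

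**Working it through.** The plan gives no coverage or precision figure to reproduce; N = 10 is stated without a derivation. The check asks what coverage 1.96 limits would have under each model form that the text allows.

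**Inputs from the protocol:** 5 per arm (IX); four visits, three of them after day 1 (Table 1); nominal 95% (XI); background prevalences: "70% of family members have symptoms of anxiety and 33% have symptoms of depression and PTSD" (VII).

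**Assumptions:** a 1.96 multiplier; random-intercept SDs of 1, 2 and 3; a true odds ratio of 1 or 0.3; an added prevalence of 50%; ordinal category shares of 40/25/20/15%.

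**1. Normal scores, arm effect averaged over visits, balanced data.** Degrees of freedom = 10 - 2 = 8, and the t multiplier is 2.306.

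- REML: coverage = P(|t8| < 1.96) = 91.4%. Width relative to the correct interval = 1.96/2.306 = 0.850.
- ML: the variance is understated by the factor 8/10, so coverage = P(|t8| < 1.96 × √0.8) = P(|t8| < 1.753) = 88.2%. Relative width = 1.753/2.306 = 0.760.
- A simulation of 200,000 trials gave 91.5% and 88.3%. With 2.306 in place of 1.96 it gave 95.0% (REML) and 92.7% (ML), so the multiplier alone does not repair ML.
- With one baseline covariate (7 df): 90.9% (REML) and 85.5% (ML).
- With 4 v 4 analysed (6 df): 90.2% and 85.9%. This matters because XVI has the forms of a withdrawn participant destroyed.

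**2. Normal scores, group-by-time contrast, random intercept, four visits.** Degrees of freedom = (10 - 2) × (4 - 1) = 24.

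- REML: P(|t24| < 1.96) = 93.8%.
- ML: P(|t24| < 1.96 × √(24/30)) = 90.8%.

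**3. Four-category ordinal logit mixed model** (400 trials in each of 12 scenarios, simulation error about 1.5 points).

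- With 1.96, coverage ran from 90.1% to 96.7%, and 7 of the 12 scenarios lay between 90.1% and 91.7%.
- With t on 8 df it ran from 94.9% to 98.0%.
- Up to 19% of trials were not estimable (1 - 0.810).

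**4. Binary logit mixed model** (1,000 trials per scenario, 1.96 limits, coverage among estimable trials).

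| Model form | Coverage |
|---|---|
| Four visits, group only | 92.7-95.4% |
| Three visits after baseline, with time terms | 94.3-98.5% |
| Group by post-baseline, day 1 as an outcome | 97.8-100% |

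About 1-61% of trials gave a separated or diverging estimate. With t on 8 df, coverage was 95.5-99.8% for the group effect and 99.6-100% for group by post-baseline, which is over-coverage.

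**5. Would a permutation interval work?** With blocks of two there are 2^5 = 32 possible allocations. The smallest two-sided p is 2/32 = 0.0625, above 0.05, so a 95% interval would be unbounded. A single block of ten gives C(10,5) = 252 allocations and a smallest p of 2/252 = 0.008.

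**The case against.** The strongest reply is that the plan prescribes neither maximum likelihood nor a 1.96 multiplier. A t-based interval is compatible with its text and would remove most of the shortfall for normal scores. That stands: the defect is an omission, and the coverage figures are conditional on how the gap is filled.

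A reader might infer that the intervals will be too narrow, at 88-91%, on whatever scale the effect is reported. The documents do not support this. The 88-91% belongs to normal scores with an identity link, while odds ratios point to a logit model. No binary scenario fell to that level; there the larger problem is estimability. Nor is 8 the right number of degrees of freedom for every contrast. Day 1 is among the repeated outcomes, so a group-by-time effect is a natural reading, and it loses less.

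A reader might also infer that the intervals miss the truth more than twice as often as stated. That fits only ML (11.8%/5% = 2.4); under REML the ratio is 8.6%/5% = 1.7. Nor does Section XI say that the interval limits feed the dissertation study. It mentions a power analysis for sample size and effect size.

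Finally, this is a feasibility study and needs no powered test. That bears on the weight of the point. It does not excuse a 95% label that the method may not deliver.

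**Conclusion.** The point holds as a gap in specification: a generalized linear mixed model in 5 v 5 spouses, 95% intervals, and no small-sample or separation method. None of the model forms examined gives dependable 95% limits from an unspecified large-sample method. With 1.96, coverage is about 88% (ML) to 91% (REML) for normal scores averaged over visits, about 90-92% in many ordinal scenarios, and about 91-94% for a group-by-time contrast with normal scores. A binary logit model is near nominal or conservative where it can be fitted, but often it cannot be.

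The normal-score figures assume balanced data and roughly normal scores. The logit figures rest on assumed random-intercept SDs, odds ratios and category shares, so they are a range and not a prediction. The weight is moderate: the change should be made, but the feasibility aim does not depend on it.

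**What to change.** State in XI:

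- **Scores.** HADS and IES scores are analysed by a linear mixed model fitted by REML, with Kenward-Roger (or Satterthwaite) degrees of freedom and t-based 95% limits, reported as mean differences. Name the contrast that is the treatment effect.
- **Ordinal outcomes kept on an odds scale.** Use t-based limits on between-participant degrees of freedom.
- **Binary outcomes, or any outcome where separation occurs.** Use a penalised or exact method, named in advance, and report how often it was needed.
- **Large-sample Wald limits** are not reported.
- **Permutation-inverted limits** are used only if the block scheme allows enough allocations, which blocks of two do not. State the block size.

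The cost is a few sentences and no new data. In the normal-score case averaged over visits, intervals become 18% wider than REML with 1.96 (2.306/1.96 = 1.18) and 32% wider than ML with 1.96 (2.306/1.753 = 1.32). Some over-coverage must be accepted in the binary case.
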